5.5.3 Withdrawal of Study Participants

Trial participants are free to withdraw from the trial at any point or can be withdrawn by the investigator. If withdrawal occurs, the primary reason for withdrawal should be documented in the participant's Case Report Form (CRF). Trial participant withdrawals will not be replaced.

If a participant discontinues study drug this does not necessarily constitute withdrawal. In this case all attempts should be made to follow up the participant as per protocol and/or re-commencing treatment (if discontinuation was due to adverse events which have subsequently resolved. Refer to section 10). It is important that all patients (with the exception of those that are withdrawn from the trial) undertake the final MRI scan at 96 weeks.

The IDMC can request trial or trial arm suspension/termination, according to the terms of the IDMC charter, for example unacceptable adverse events.

Sponsor No.12/0219 v7 Page **37** of **73**

6 INVESTIGATIONAL MEDICINAL PRODUCT AND PLACEBO

6.1.1 Treatment Allocation

Following randomisation study drug will be dispensed by the site pharmacy. Patients will be randomised to one of the following arms:

- Fluoxetine 20 mg twice per day (20 mg once per day for first 4 weeks)
- Riluzole 50 mg twice per day (50 mg once per day for first 4 weeks)
- Amiloride 5 mg twice per day (5 mg once per day for first 4 weeks)
- Matched placebo twice per day (1 capsule a day for first 4 weeks)

6.1.2 Name and description of investigational medicinal products

Investigational drugs for this trial: (NB other brands using the same active substances will not be used).

Riluzole (RILUTEK 50 mg film-coated tablets)

Riluzole is a member of the benzothiazole class. Chemically, riluzole is 2-amino-6-(trifluoromethoxy) benzothiazole. Its molecular formula is $C_8H_5F_3N_2OS$ and its molecular weight is 234.2 Riluzole is a white to slightly yellow powder that is very soluble in dimethylformamide, dimethylsulfoxide and methanol, freely soluble in dichloromethane, sparingly soluble in 0.1 N HCl and very slightly soluble in water and in 0.1 N NaOH. RILUTEK (riluzole) is available as a capsule-shaped, white, film-coated tablet for oral administration containing 50 mg of riluzole. Each tablet is engraved with "RPR 202" on one side. The Marketing Authorisation Holder is Aventis MA EU/1/96/010/001. For the purpose of the trial commercial Rilutek will be over-encapsulated by a third party manufacturer holding a MIA IMP in conformance with EU cGMP, in order to achieve the blinding.

Amiloride HCI

Amiloride is an antikaliuretic-diuretic agent, a pyrazine-carbonyl-guanidine that is unrelated chemically to other known antikaliuretic or diuretic agents. It is the salt of a moderately strong base (pKa 8.7). It is designated chemically as 3, 5- diamino-6-chloro- N-(diaminomethylene) pyrazinecarboxamide monohydrochloride, dihydrate and has a molecular weight of 302.12. Its empirical formula is $C_6H_8CIN_7O$ -HCl-2H₂O. Each tablet for oral administration contains 5 mg of Amiloride HCl, calculated on the anhydrous basis. For the purpose of the trial commercial Amiloride will be over-encapsulated by a third party manufacturer holding a MIA IMP in conformance with EU cGMP, in order to achieve the blinding.

Fluoxetine

Fluoxetine hydrochloride is a selective serotonin re-upake inhibitor. It is designated (±)-N-methyl-3-phenyl-3-[(a,a,a-trifluoro-p-tolyl)oxy]propylamine hydrochloride and has the molecular formula of C17H18F3NO•HCI. Its molecular weight is 345.79. Fluoxetine hydrochloride is a white to off-white crystalline solid with a solubility of 14 mg/mL in water.

Fluoxetine 20mg capsules will be over-encapsulated by a third party manufacturer holding a MIA IMP in conformance with EU cGMP, in order to achieve the blinding.

Placebo

Identical placebo to match the 3 active drugs will be manufactured by the same manufacturer overencapsulating the IMPs. An equivalent amount of inert excipient will be used in place of the active ingredients. The placebo will be packaged for the trial by a MIA IMP holder third party manufacturer in UK. The blinding will be achieved by over-encapsulation of the IMP and producing an identical placebo. Further detail is given in section 6.3 and 6.4.

6.1.3 Labelling, packaging and storage

The trial drug will be stored below 25°C in a dry place and protected from light. All active and placebo will be packaged by the MIA IMP holder UK third party manufacturer in Polyethylene Bottles containing the same number of capsules.

Labelling will be in a blinded fashion and in accordance to requirements of EU GMP Annex 13. In order to maintain blinding, bottles will be coded and both shelf life and storage conditions will be adjusted to maintain blinding.

6.1.4 **Dispensing, handling and drug accountability**

The bottles will be dispensed according to site and study-specific SOPs by the local site pharmacy. During the study a subject specific accountability log will be kept to record each dose of the trial drug dispensed for each trial participant. These logs will be monitored. All used returned bottles will be kept for potential reconciliation by the sponsor; they will be discarded by the research staff according to local procedures, upon authorisation from the sponsor.

The **Drug Accountability Log** must be completed to record each dose of the trial drug dispensed for each trial participant.

6.1.5 Summary of Product Characteristics (SmPC) or Investigators Brochure

For fluoxetine, and amiloride, (both IMPs provided by Actavis) and riluzole (Rilutek, provided by Sanofi) the latest SmPC will be used as their reference document and this can be accessed from electronic medicines compendium: www.medicines.org.uk/

6.2 PLACEBO

The MS-SMART placebo comprises a size 00 capsule identical to the over-encapsulated Fluoxetine/Amiloride/Riluzole. The trial medications are described in Section 6.1.2.

6.3 DOSING REGIME

Following randomisation, study drug will be dispensed by the site pharmacy.

Patients are prescribed 1 capsule a day (OD), orally at baseline. At 1 month they will up-titrate to 1 capsule twice a day (bd) orally for the remainder of the study; no relationship to food is required.

That is:

- Fluoxetine 20 mg twice per day (20 mg once per day for first 4 weeks)
- Riluzole 50 mg twice per day (50 mg once per day for first 4 weeks)
- Amiloride 5 mg twice per day (5 mg once per day for first 4 weeks)
- Placebo –1 capsule twice per day (1 capsule once per day for first 4 weeks)

6.4 DOSE MODIFICATION AND STOPPING RULES

The following terms will be used:

MS-SMART Version 7 4th June 2018

- 'Full dose' 1 capsule TWICE a day.
- 'Half dose' 1 capsule ONCE a day.
- 'Zero dose' 0 capsules taken.

As the trial is blinded, participants will not know which treatment they are on.

At Baseline:

Participants will be prescribed the 'half dose' for the first 4 weeks.

At 4 Weeks:

Participants will up-titrate to 'full dose' for the remainder of the study.

Dose Modification (if required) – Baseline to Week 4:

If a participant cannot tolerate the 'half dose' (duration according to the Investigator's discretion) the dose should be stopped ('zero dose'). The participant will be re-challenged 2-4 weeks later with the 'half dose' at the discretion of the PI. The participant should then take the 'half dose' for 4 weeks before up-titrating to the 'full dose'.

If however, the participant cannot tolerate the 'half dose' when re-challenged (duration according to local PI discretion), the participant should be off medication for the remaining duration of the trial. The participant will remain in trial follow-up.

Dose Modification as a result of Adverse Events:

At the discretion of the local PI the participant can down-titrate to 'half dose' if Adverse Events (AEs) occur. This does not preclude the participant increasing the dose subsequently (up to the week 24 visit) to the 'full dose'.

If a participant cannot tolerate the 'half dose' (duration according to the Investigator's discretion) the dose should be stopped ('zero dose'). The participant can be re-challenged 2-4 weeks later with the 'half dose' at the discretion of the PI. If they cannot tolerate the 'half dose' again (duration according to local PI discretion) the participant should be off medication for the remaining duration of the trial. The participant will remain in trial follow-up.

If a participant cannot tolerate the 'full dose' (duration according to the Investigator's discretion), the dose should be reduced to 'half dose'. The participant will be re-challenged at 2-4 weeks later. If they cannot tolerate the 'full dose' again (duration according to local PI discretion), they should reduce to 'half dose'. The participant will be re-challenged a second time 2-4 weeks later with the full dose. If the participant cannot tolerate that dose again (duration according to the Investigator's discretion) they should reduce to the half dose for the remaining duration of the trial.

At the Investigator's discretion, participants can be re-challenged with a higher dose a maximum of 2 times. The participant's dose must be fixed at or by the week 24 visit for the remaining duration of the study (unless in response to managing AEs).

A full record of medication administered will be kept.

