Rare serious side-effects: Patients with a history of suicide-related events, or those exhibiting a significant degree of suicidal ideation prior to commencement of treatment are known to be at greater risk of suicidal thoughts or suicide attempts, and should receive careful monitoring during treatment.

Mitigation-patients with significant depression are excluded.

Rash and allergic reactions: Rash, anaphylactoid events and progressive systemic events, sometimes serious (involving skin, kidney, liver or lung), have been reported.

Patients will stop medication if there is any evidence of progressive and worsening skin reaction.

Sponsor No.12/0219 v7 Page **20** of **73** *Seizures:* Seizures are a potential risk with antidepressant drugs. Patients with a history of seizures (epilepsy) are excluded.

Mania: Antidepressants should be used with caution in patients with a history of mania/hypomania. As with all antidepressants, fluoxetine should be discontinued in any patient entering a manic phase.

Hepatic/Renal function: Fluoxetine is extensively metabolised by the liver and excreted by the kidneys.

To enter the trial normal renal and hepatic function is required and is monitored. The IMP is stopped if >3ULN.

Cardiovascular Effects: Cases of QT interval prolongation and ventricular arrhythmia including torsades de pointes have been reported during the post-marketing period. Fluoxetine should be used with caution in patients with conditions such as congenital long QT syndrome, a family history of QT prolongation or other clinical conditions that predispose to arrhythmias (e.g., hypokalemia, hypomagnesemia, bradycardia, acute myocardial infarction or uncompensated heart failure) or increased exposure to Fluoxetine (e.g., hepatic impairment). If patients with stable cardiac disease are treated, an ECG review should be considered before treatment is started. If signs of cardiac arrhythmia occur during treatment with Fluoxetine, the treatment should be withdrawn and an ECG should be performed. As recruitment for this study has now been completed, the eligibility criteria will not be amended to exclude patients with known congenital or family history of long QT syndrome or any clinical conditions that predispose them to arrhythmias.

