Diabetes: In patients with diabetes, treatment with an SSRI may alter glycaemic control. Hypoglycaemia has occurred during therapy with fluoxetine and hyperglycaemia has developed following discontinuation. Insulin and/or oral hypoglycaemic dosage may need to be adjusted.

Care will be taken to monitor the glycaemic control as part of normal care and where required any dose adjustments to diabetic medication will be at the discretion of the treating physician.

Akathisia/psychomotor restlessness: The use of fluoxetine has been associated with the development of akathisia, characterised by a subjectively unpleasant or distressing restlessness and need to move, often accompanied by an inability to sit or stand still.

Clinical monitoring of the participant's mental state will occur at study visits throughout trial.

If akathisia/psychomotor restlessness occurs the drug will be discontinued.

Haemorrhage: There have been reports of cutaneous bleeding abnormalities, such as ecchymosis and purpura with SSRIs. Ecchymosis has been reported as an infrequent event during treatment with fluoxetine. Other haemorrhagic manifestations (e.g., gynaecological haemorrhages, gastro-intestinal bleedings and other cutaneous or mucous bleedings) have been reported rarely. Caution is advised in patients taking SSRIs, particularly in concomitant use with oral anticoagulants, drugs known to affect platelet function (e.g., atypical antipsychotics, such as clozapine, phenothiazines, most TCAs, aspirin, NSAIDs), or other drugs that may increase risk of bleeding, as well as in patients with a history of bleeding disorders.

Electroconvulsive therapy (ECT): There have been rare reports of prolonged seizures in patients on fluoxetine receiving ECT treatment. Patients will be excluded from the trial with bipolar disorder/previous ECT. If ECT is needed during the trial, participants will discontinue drug.

St John's Wort: An increase in serotonergic effects, such as serotonin syndrome, may occur when selective serotonin reuptake inhibitors and herbal preparations containing St John's Wort (*Hypericum perforatum*) are used together. St John's Wort is contraindicated during the trial.

Sponsor No.12/0219 v7 Page **21** of **73** CYP2D6 isoenzyme inhibitors: (such as flecanide, encainide, carbamazepine and trycyclic antidepressants), should be initiated at or adjusted to the low end of their dose range.

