On rare occasions, development of a serotonin syndrome or neuroleptic malignant syndrome-like events have been reported in association with treatment of fluoxetine, particularly when given in combination with other serotonergic (among others, L-tryptophan) and/or neuroleptic drugs. As these syndromes may result in potentially life-threatening conditions, treatment with fluoxetine should be discontinued if such events (characterised by clusters of symptoms, such as hyperthermia, rigidity, myoclonus, autonomic instability with possible rapid fluctuations of vital signs, mental status changes, including confusion, irritability, extreme agitation, progressing to delirium and coma) occur and supportive symptomatic treatment should be initiated. The risk of this is very low and was not reported in the two phase IIa clinical studies of fluoxetine in multiple sclerosis.^{18, 20}

Drug withdrawal: The SPC reports that withdrawal symptoms when treatment is discontinued are common, particularly if discontinuation is abrupt. In previous phase IIa clinical studies of fluoxetine in multiple sclerosis ¹⁸ ²⁰ they did not report any withdrawal reactions upon discontinuation of long term use of Fluoxetine. Based on these previous studies^{18, 20}, gradual dose reduction in this protocol will not occur on the last treatment visit, however, participants will be followed by telephone 1 month after terminating the study to ascertain any issues with terminating the medication Participants are also reminded in the Participant Information Leaflet (PIL) to contact the study team if there are any withdrawal symptoms.

Risk minimisation: standard monitoring and treatment of nausea, diarrhoea and headache will be provided as needed. Patients with renal failure or hepatic failure are excluded from the trial. If clinically significant LFT changes occur during the trial, or creatinine>130mmol/l, the steps outlined in section 6.7.3 (Management of Laboratory Abnormalities) will be followed. FBC monitoring (including neutrophil count) is part of the safety blood panel, and the steps outlined in section 6.7.3 will take place if the neutrophil level falls below <1.0 x10⁹ /l or the platelet level reduces to <50 x10⁹ /l.

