Risk minimisation: patients with renal failure or hepatic failure are excluded from the trial. If clinically significant LFTs occur during the trial, the steps outlined in section 6.7.3 will be followed. FBC (including neutrophil count) is part of the safety blood panel, and the steps outlined in section 6.7.3 will take place if the neutrophil level falls below <1.0 $\times 10^9$ /l. The report of a febrile illness should prompt physicians to check white blood cell counts and to discontinue riluzole in case of neutropenia. If respiratory symptoms develop such as dry cough and/or dyspnoea, chest radiography should be performed, and in case of findings suggestive of interstitial lung disease (e.g. bilateral diffuse lung opacities), riluzole should be discontinued immediately. In the majority of the reported cases, symptoms resolved after drug discontinuation and symptomatic treatment.

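### Section 1.2.2 and the operational sections 5.5.3, 6.4 and 6.6.4 give unreconciled instructions on stopping treatment after named adverse events and laboratory findings

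*Protocol*

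**What the plan says.** **Section 1.2.2 (drug rationale and safety).** Under fluoxetine (1.2.2.1):
- Skin: "Patients will stop medication if there is any evidence of progressive and worsening skin reaction".
- Restlessness: "If akathisia/psychomotor restlessness occurs the drug will be discontinued".
- Mania: "fluoxetine should be discontinued in any patient entering a manic phase".
- Arrhythmia: "If signs of cardiac arrhythmia occur during treatment with Fluoxetine, the treatment should be withdrawn and an ECG should be performed".
- Serotonin or neuroleptic-malignant-like syndrome: "treatment with fluoxetine should be discontinued if such events" occur.
- Liver and kidney function: the study drug is stopped above 3 times the upper limit of normal (ULN).

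Under riluzole (1.2.2.2), findings that suggest interstitial lung disease mean that "riluzole should be discontinued immediately". Riluzole is also to be discontinued if neutropenia is found when a febrile illness is worked up.

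**Section 6.4 (dose modification and stopping rules).** The general adverse-event rule lets the local investigator go to half dose at discretion. If the half dose is not tolerated, dosing stops and re-challenge is optional. If the full dose is not tolerated, the dose drops to half and "The participant will be re-challenged at 2-4 weeks later". A second re-challenge follows if that fails, and the branch ends at half dose. The section closes by making re-challenge at a higher dose discretionary, at most twice.

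**Section 5.5.3.** After study drug is discontinued, attempts are to be made at follow-up and/or "re-commencing treatment (if discontinuation was due to adverse events which have subsequently resolved". No event is excepted.

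**Section 6.6.4 (laboratory abnormalities).** Above 3 times ULN, if a repeat confirms it, reduction or stopping is considered; discontinuation is recommended above 5 times ULN. For neutrophils below 1.0 x10⁹/l, medication is suspended, the count is repeated and re-challenge is considered if it improves.

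**The concern.** The section whose title promises stopping rules names none of the clinical events that section 1.2.2 says end treatment, and does not refer back to them. For some events the two places give opposite actions. A site that works from section 6.4 could return a participant to the full dose after an event for which section 1.2.2 calls for a stop.

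Blinding adds to this. Several stop rules in section 1.2.2 are tied to a drug name, and the site sees only identical capsules. Section 6.6.3 meets the same problem for contraindicated medicines by pooling them across all arms. Nothing in the protocol does so for these stop rules. At stake is participant safety and uniform conduct across sites.

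**Working it through.** No sample size, power or error rate enters this point. The check sets the passages side by side and separates directive wording (*will*, *is*) from softer wording (*should*, *can*, at discretion).

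| Trigger | Section 1.2.2 | Operational text | Result |
|---|---|---|---|
| Progressing skin reaction | *will* stop; arm-neutral | 6.4: if not tolerated on full dose, half dose and *will* be re-challenged | Direct conflict on that branch |
| Akathisia | *will* be discontinued; arm-neutral | 6.4: as above | Direct conflict on that branch |
| Mania | *should* be discontinued; fluoxetine named | 6.4: not mentioned | Missing exception |
| Arrhythmia | *should* be withdrawn; fluoxetine named | 6.4: not mentioned | Missing exception |
| Serotonin or neuroleptic-malignant-like syndrome | *should* be discontinued; fluoxetine named | 6.4: not mentioned | Missing exception |
| Interstitial lung disease | *should* be discontinued at once; riluzole named | 6.4: not mentioned | Missing exception |
| Liver tests above 3 x ULN | *is* stopped; arm-neutral | 6.6.4: reduction or stopping considered if confirmed; discontinuation recommended above 5 x ULN | Direct conflict between 3 and 5 x ULN |
| Neutropenia | discontinue; riluzole named | 6.6.4: suspend, repeat, consider re-challenge | Conflict, with the caveat under the objection |

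**Count.** 2 + 4 + 2 = 8 triggers. Four conflict directly (skin, akathisia, liver, neutropenia) and four lack an exception. Five are worded by drug name (mania, arrhythmia, serotonin or neuroleptic-malignant-like syndrome, lung disease, neutropenia); three are arm-neutral.

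**Where the full-dose branch of 6.4 ends.** Full dose fails, half dose, first re-challenge; fails, half dose, second re-challenge; fails, half dose to the end of the trial. This branch contains no stop. The half-dose branch does reach zero dose and can end with the participant off medication.

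**Inside 6.4.** The full-dose branch says *will*; the closing paragraph leaves re-challenge at a higher dose to the investigator. These two also need aligning.

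**Does discontinued mean for good?** Section 6.6.4 separates suspending from discontinuing, which suggests finality. Section 5.5.3 uses discontinuation for something that can be reversed. The protocol does not settle it.

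**Cross-references.** Sections 1.2.2.1, 1.2.2.2 and 1.2.2.3 send the reader to section 6.7.3 for laboratory management. Those rules are numbered 6.6.4. Section 5.5.3 points to section 10, which repeats none of the stop rules.

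**Scale.** The protocol gives no rates for most triggers. It calls the serotonin or neuroleptic-malignant-like risk very low and lists neutropenia and interstitial lung disease as rare. For liver tests it cites an ALS study with increases in 10% of the 100 mg/day group. If that rate carried over, 0.10 x 110 = 11 riluzole participants would have a raised test. That is an upper limit for the conflicting band in that arm, because the protocol does not say how many fall between 3 and 5 x ULN.

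**The case against.** The strongest reply is that a reader might infer more than the text says, in three respects.

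1. *That section 6.4 answers every adverse event with half dose and re-challenge.* It does not. The general rule is *can*, at the investigator's discretion; the directive wording covers only intolerance of the full dose.
2. *That treatment ends only after a failed half-dose re-challenge.* It does not. In the adverse-event part, re-challenge from zero dose is optional, so a first stop can be final. Section 5.5.3 lets the investigator withdraw a participant, and its and/or wording means follow-up alone complies. Nothing in section 6.4 forbids stopping under section 1.2.2.
3. *That exposure is no longer comparable by arm.* The documents do not support this. Sites are blinded and site is a minimisation variable, so differing site practice is spread across arms. The primary analysis is by randomised group irrespective of treatment taken and adjusts for centre.

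These three replies stand. Others stand in part:
- Three triggers are already arm-neutral, section 10.4 assesses events as if on active drug, and section 5.5.2 allows emergency unblinding. Five rules still carry a drug name, and routine conduct should not depend on breaking the blind.
- Section 1.2.2.2 itself refers neutrophils below 1.0 x10⁹/l to the laboratory section before giving the febrile-illness rule. The two could be meant for different situations, but the text does not say so.
- Section 6.4 limits return to full dose to the week 24 visit and fixes the dose by then, adverse-event management excepted. Section 1.2.2.1 says recruitment is complete. From this version (4 June 2018) to the planned end (31 October 2018) is 149 days, or 149/7 = 21.3 weeks. With 100 weeks per participant, anyone remaining would be at about week 100 - 21.3 = 78.7 or later, if those dates held. This narrows practical exposure. It does not remove the liver, neutropenia or restart provisions, which have no time limit.

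**Conclusion.** The point holds in a limited form. Section 1.2.2 and the operational sections are not reconciled on stopping treatment. The conflict is direct in the full-dose re-challenge branch of section 6.4 (firmest for skin reaction and akathisia, where both sides say *will*) and in the laboratory rules (liver tests between 3 and 5 x ULN, and neutropenia). For mania, arrhythmia, serotonin or neuroleptic-malignant-like syndrome and interstitial lung disease, the defect is a missing exception or cross-reference.

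This rests on two assumptions: that an event named in section 1.2.2 can also be handled as intolerance of the full dose, which section 6.4 does not exclude, and that sites take stopping rules from the section so titled, which is inferred from the title. The number of participants affected cannot be derived from the protocol. The matter is one of participant safety and consistent conduct; no bias in the primary comparison is shown.

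**What to change.** Reconcile sections 1.2.2.1, 1.2.2.2, 5.5.3, 6.4 and 6.6.4:

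- List the named events once in section 6.4, worded for a blinded capsule so that the rule applies in every arm. State for each whether the discontinuation instruction or the reduce-and-re-challenge path governs, and whether discontinuation is permanent.
- Align the directive and discretionary wording on re-challenge within section 6.4.
- State in section 5.5.3 whether restarting applies to the listed events.
- Make sections 1.2.2 and 6.6.4 agree on liver tests and neutropenia, or state that they cover different situations.
- Correct the references to section 6.7.3 so that they point to 6.6.4.

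The clinical team decides which action stands for each event. The cost is protocol wording and a site memo, with no extra visits, tests or participants. If discontinuation is chosen, a few more participants may stop for good; they would stay in follow-up and, where scanned, in the primary analysis.
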